### 4.2.3 Acceptability

All audio-recorded interviews will be transcribed and translated into English (as necessary). Transcripts will be uploaded into MAXQDA software for coding and analysis. All documents will first be coded by participant stratification (engaged vs. not engaged in care) and personal characteristics to allow for a search of documents and comparisons that explore differences among participants, regional patterns, and clinic specific characteristics. This will be followed by inductive and deductive coding based on a coding guide that reflects key analytic concepts, including stigma, social capital, and access to health care.

Qualitative analysis will proceed by first listing variations in care experiences among study participants, and then explore similarities and differences in these experiences between

different types of patients. Particular attention will be paid to how participants in the TCAC arm talk about HIV care, stigma management, and the role of the TCAC in addressing these issues. Qualitative analysis will then explore the positive and negative experiences with health care providers; who they identify as trustworthy; and how they describe the role of family, friends, community members, and health care providers in supporting or impeding their efforts to access health care. Analysis will also assess whether participants have unmet needs and barriers to services, including level of comfort receiving services in different settings, experience navigating health and social service bureaucracies, instances of failure to follow up with care, and continuing unmet needs.

## 5 Data Management

---

Data will be collected to review study associated outcomes in order to evaluate the extent to which the case management goals and objectives are being met. To achieve this, data will be collected in the pre- and intervention study periods. In addition to this, data will also be collected to assess actual programme performance against planned activities.

### 5.1 Data collection tools

**Table 5: List of data collection tools and intended use**

Name of tool	Purpose	Schedule	Study arm
Visit Contact Documentation (AD001)	To collect and track information on all study contacts made with the participant during scheduled visit windows.	Pre-release Post-release	CAU TCAC
Pre-release locator Form (AD002)	To collect the participant's personal information important for identifying and contacting the participant for follow up after release.	Pre-release	CAU TCAC
Release Verification (AD003)	To verify participant release from the correctional facility and collect information of the documented date of release.	Post-release	CAU TCAC
Post-release locator Form (AD004)	To collect the participant's personal information important for identifying and contacting the participant for follow up after release.	Pre-release	CAU TCAC
Off Study (AD005)	To document discontinued participation in the study due to withdrawal, loss to follow up or end of the study procedures.	Pre-release Post-release	CAU TCAC
Screening, Eligibility & Enrolment (EL001)	To collect screen participant for eligibility, and collect enrolment information.	Pre-release	CAU TCAC

Baseline Demographics (DM001)	To collect participant demographic information at the time of enrolment	Pre-release	CAU TCAC
Demographics Follow-Up (DM002)	To update participant demographic information (where necessary) after correctional facility release.	Post-release	CAU TCAC
Pre-release Assessment (RK001)	To collect information on health and ART history, ASSIST substance use (alcohol and other drugs) screen, PHQ-9 depression screen, social capital, and stigma screens)	Pre-release	CAU TCAC
Post-release Assessment (RK002)	To collect information on health and ART history, ASSIST substance use (alcohol and other drugs) screen, PHQ-9 depression screen, social capital, and stigma screens)	Post-release	CAU - Day 30 visit TCAC- at first session
Routine Health Screening (RK003)	To closely monitor participant health status in order to guide referrals and session services following established study algorithms (includes symptom screen, and weight measurements).	Post-release	TCAC
Health Seeking (SS001)	To collect information on self-reported visits to access medical or non-medical HIV care and treatment services at any time after correctional centre release.	Post-release	CAU TCAC
Clinic Visit (SS002)	To collect details of self-reported participant clinic visits.	Post-release	CAU TCAC
No Clinic Visit (SS003)	To document the reasons for non-entry among participants who self-report that they have not gone to the clinic.	Post-release	CAU TCAC Self-reporting no clinic visits.
Post-entry (SS004)	To document information on additional clinic visits made by the participant after initial entry-into-care	Post-release	CAU TCAC Self-reported clinic visits.
Case note abstraction pre-release (FV001)	To abstract information on participant health and ART history reviews from correctional facility clinical management records.	Pre-release	CAU TCAC
Case note abstraction post-release (FV002)	To verify self-reported clinic visits or identify unreported clinic visits (among participants that cannot be contacted from electronic health record sources), and abstract information on participant health and clinic management in community clinics.	Pre-release	CAU TCAC

Laboratory Testing (LT001)	To document collection of lab specimens and results for HIV RNA, creatinine and CD4 counts.	Post-release	CAU TCAC
TCAC Transition (TR001)	To document transition of participants out of the TCAC.	Post-release	TCAC

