### 2.3.1 Inclusion criteria

- Currently incarcerated (either an offender (sentenced inmates) or awaiting trial inmate (un-sentenced))
- Housed at Modderbee or Kgosi Mampuru II Correctional Centres (including participating satellite centres)
- Diagnosed with HIV
- Currently receiving ART
- Anticipated release or trial date within 3 months of study enrollment
- Self-report expected to reside within Ekurhuleni, Tshwane, or Johannesburg districts of Gauteng Province and within proximity to one of the TCAC sites (within 20km, 45 minute travel time, or two local taxi minibus rides)
- Agree to post-discharge follow-up
- Medically stable based on DCS health assessment
- On ART for  $>3$  months at the expected time of corrections release

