## 2.7.3 Care verification

Clinical records will be accessed to determine linkage to care status, timing of linkage to care, ART continuation, retention in care, and HIV RNA results. This will be done through reviewing paper clinic charts, electronic clinic data (tier.net), and electronic laboratory data (NHLs Trackcare system). Linkage between participants and records will be based on matching surname, first name, date of birth, sex, and appropriate date range.

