### 2.8.4 TCAC eligibility

All study participants assigned to the TCAC arm will be eligible for the TCAC. This includes individuals who may not meet community adherence club eligibility criteria. The reason for this approach is that, at present, there is low linkage to care from corrections. Furthermore, those individuals with the greatest adherence and clinic attendance challenges are hypothesized to benefit the most from the TCAC interventions. Thus all released inmates who meet the enrollment criteria will be eligible for TCACs – this is a critical component of the study.

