## 2.9.2 Effectiveness of TCACs

**Primary outcome:** The primary outcome of this assessment is the proportion of participants with self-reported care at 6 months either in TCAC or DoH clinical care. Self-reported care at 6 months will be defined as – having at least two post-release HIV care visits 90 days apart with the last visit between 5 and 7 months from release. We will perform an analysis of retention in care at 6 months among all randomized individuals as an intent to treat analysis.

We will also perform an eligible for 6 month follow-up analysis. This analysis will exclude:

- Not released within 3 months of enrollment
- Re-incarcerated within 6 months of release
- Died within 6 months of release
- Withdrawn participation within 6 months of release

**Secondary outcomes:** We will also evaluate the effectiveness of TCACs compared to care-as-usual for the following secondary outcomes:

1. Verified in care at six months
2. Time to linkage to care
3. Linkage to care within 90 days of corrections release
4. HIV RNA <400 c/mL at 6 months - Viral load data at 6 months will be based on routinely collected viral load data (clinic records and the electronic National Health Laboratory System to determine 6 month viral load outcomes, successfully applied in prior studies) augmented by viral loads obtained by the study when 6 month viral load data are not available.
5. Social capital score change
6. Stigma index score change
7. Employment or self-employment

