**Table 3: Effectiveness outcomes**

Primary outcome	Self-reported in care at six months by arm	Test of proportions (chi-square)
Secondary outcomes	Self-reported linkage to care by 90 days by arm	Test of proportions (chi-square)
	Clinical record verified in care at six months by arm	Test of proportions (chi-square)
	HIV RNA <400c/mL for those in care by arm	Test of proportions (chi-square)
	Social capital score by arm	Test of medians (Wilcoxon rank sum)
	Stigma index score by arm	Test of medians (Wilcoxon rank sum)
	Employed or self-employed by arm	Test of proportions (chi-square)

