## 5.2 Schedule of case report forms

Table 6: Schedule of data collection within correctional facility

Case Report Form	Form Code	Visits:	Visit 1 Enrolment	Visit 2 Pre-release
		Visit Code:	01.0	02.0
Screening, Eligibility & Enrolment	EL001		X	
Pre-release assessment	RK001		X	
Baseline Demographics	DM001		X	
Visit Contact Documentation	AD001		X	[X]
Pre-release Locator	AD002		X	
Case Note Abstraction Pre-release	FV001		[X]	[X]

X required CRF, [X] may be required if updated or as necessary

Table 7: Scheduled study visit windows for all participants after release from correctional facility

Case Report Form	Form Code	Visits:	Visit 3 Release	Visit 4 Post- release	Visit 5 Post- release	Visit 6 Post- release	Visit 7  Post-release
		Time since release:	0D	30D	900D	182D	90 days from time of entry
		Visit Code:	03.0	04.0	05.0	06.0	07.0
Release verification	AD003		X				
Post-release locator	AD004			[X]	[X]	[X]	
Demographics Follow-Up	DM002			[X]	[X]	[X]	
Health Seeking	SS001			[X]	[X]	[X]	
Clinic Visit	SS002			[X]	[X]	[X]	
HIV/TB Testing	SS003			[X]	[X]	[X]	

No Clinic Visit	SS004			[X]	[X]	[X]	
Post entry into care	SS005						X
Case Note Abstraction Post-release	FV002			[X]	[X]	[X]	[X]
Off Study	AD002			[X]	[X]	[X]	[X]

X required CRF, [X] may be required if updated or as necessary

Visit 7 only occurs if participant had entered into care by Visit 7

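### The plan does not guarantee a pre-release HIV RNA value for the six-month HIV RNA <400 c/mL outcome; recording one from existing records would be a cheap improvement

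*Combined protocol and SAP*

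**What the plan says.** **Outcome.** Sections 1.2 and 2.9.2 list HIV RNA <400 c/mL at six months as a secondary outcome. Section 2.9.2 gives the source: "Viral load data at 6 months will be based on routinely collected viral load data", supplemented by study samples where no routine result exists. Table 3 narrows the comparison to "HIV RNA <400c/mL for those in care by arm" and assigns a chi-square test. Section 4.2.2 instead describes an intention-to-treat mixed effects logistic regression for effectiveness. Section 1.2 makes retention with an undetectable viral load the primary outcome of the future full trial.

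**Entry.** Section 2.3.1 asks for current ART, more than three "months at the expected time of corrections release", and "Medically stable based on DCS health assessment". It sets no viral load threshold and does not define stability. Section 2.8.4 is deliberately broad: "This includes individuals who may not meet community adherence club eligibility criteria".

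**Pre-release data.** In Table 5, FV001 serves "To abstract information on participant health and ART history reviews from correctional facility clinical management records". Table 6 marks it [X] at both enrolment and the pre-release visit; the key reads "X required CRF, [X] may be required if updated or as necessary". The forms marked X at enrolment are EL001, RK001, DM001, AD001 and AD002, and none is described as holding a viral load. The only form whose description names HIV RNA is LT001, scheduled after release.

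**Record search.** Section 2.7.3 covers paper charts, tier.net and the laboratory system: "Clinical records will be accessed to determine linkage to care status, timing of linkage to care, ART continuation, retention in care, and HIV RNA results". It sits under post-release follow-up.

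**The concern.** The TCAC is meant to prevent loss of care after release. A six-month viral load on its own mixes two things: suppression lost after release, and viraemia already present in custody. The entry criteria permit the second, and the plan secures no value that would separate them.

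Three things are at stake:

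- **Precision.** A likely strong predictor of the outcome is not available for adjustment, and chance imbalance in it cannot be checked.
- **The in-care comparison.** Being in care at six months is a post-randomisation event. Section 2.8.4 hypothesises that people with the greatest adherence difficulties benefit most. If the TCAC keeps more of them in care, the two in-care groups could differ systematically in pre-release viraemia.
- **Planning.** The full trial's intended primary outcome includes viral load. The pre-release suppression rate, and how often records contain it, are inputs that a pilot could supply.

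**Working it through.** **1. The plan's own figure.** Section 4.1 gives 60 and 120 participants, 78% ascertainment, 0.25 versus 0.49, alpha 0.05 and 80% power. The analysed numbers are 60 × 0.78 = 46.8 and 120 × 0.78 = 93.6. With a two-sided test (assumed) and pooled variance:

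- pooled rate = (0.25 + 2 × 0.49)/3 = 0.41
- null SE = sqrt(0.41 × 0.59 × (1/46.8 + 1/93.6)) = 0.0881
- alternative SE = sqrt(0.25 × 0.75/46.8 + 0.49 × 0.51/93.6) = 0.0817
- z = (0.24 − 1.96 × 0.0881)/0.0817 = 0.825, so power is 79.5%

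The stated power reproduces. Nothing in this point changes it, because the fix alters data collection and not sample size.

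**2. Chance imbalance at release, by analysis set.** The documents give no prevalence of viraemia at release, so v is assumed. The 95% range for the chance difference between arms is ±1.96 × sqrt(v(1−v)(1/n1 + 1/n2)), in percentage points:

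| v | 60 / 120 | 46.8 / 93.6 | 11.7 / 45.9 (in care, illustrative) |
|---|---|---|---|
| 10% | ±9.3 | ±10.5 | ±19.3 |
| 20% | ±12.4 | ±14.0 | ±25.7 |
| 30% | ±14.2 | ±16.1 | ±29.4 |

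The last column uses 46.8 × 0.25 = 11.7 and 93.6 × 0.49 = 45.9. Those rates are the plan's for care plus undetectable viral load, so the in-care numbers could be larger. The 44% ART continuity in section 1.1 would give 46.8 × 0.44 = 20.6 in the CAU arm. The column shows chance alone; any systematic difference from selection into care would come on top.

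**3. Effect on the all-randomised comparison (60/120).** Assume the baseline-suppressed are 30-50 points more likely to be suppressed at six months. The imbalance then moves the observed difference by 0.093 × 0.3 = 0.028 up to 0.142 × 0.5 = 0.071, or about ±3 to ±7 points. This is part of ordinary sampling error and already lies inside the unadjusted interval.

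**4. Gain from adjustment.** Let p be the share suppressed at release (0.7-0.9), a = 0.85 the six-month suppression in those suppressed at release, b = 0.55 or 0.35 in the others, and m = pa + (1−p)b. All are assumed. Then R² = p(1−p)(a−b)²/(m(1−m)).

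- Smallest: p = 0.9, b = 0.55, m = 0.82; R² = 0.09 × 0.09/0.1476 = 0.055
- Largest: p = 0.7, b = 0.35, m = 0.70; R² = 0.21 × 0.25/0.21 = 0.25

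The unadjusted half-width is 1.96 × sqrt(m(1−m) × 0.025): ±12 points at m = 0.82 and ±14 at m = 0.70. As an approximation, adjustment scales it by sqrt(1−R²) = 0.972 to 0.866, so it is about 3-13% narrower.

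**5. Interpretation.** If a share q of those viraemic at release remain so, and a share f of the suppressed become viraemic, the part of six-month viraemia already present at release is vq/(vq + (1−v)f). With assumed v = 5-30%, q = 0.5-0.8 and f = 0.2-0.4, this runs from 0.025/0.405 = 6% to 0.24/0.38 = 63%. Without pre-release values the trial cannot say where in that range it lies.

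**The case against.** A reader might infer that viraemia at release cannot be told from viraemia after lost care, or that the suppression comparison is biased. The documents support neither.

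- **The form contents are not shown.** RK001 is required at enrolment and covers health and ART history, so it may hold a viral load. FV001 may too: one-line purposes in Table 5 do not prove that a field is absent. FV002's purpose does not name HIV RNA either, although section 2.7.3 plans to take HIV RNA from clinical records. This stands: the value is not guaranteed, which is weaker than unavailable.
- **The [X] mark does not mean optional.** Table 7 gives it to SS001 and SS002, which record the self-reported visits behind the primary outcome. This stands as a caution; the mark still does not make FV001 required.
- **Randomisation balances pre-release viraemia in expectation.** This stands for the all-randomised comparison. It does not carry over to the in-care subset.
- **The Table 3 test leaves out people who have lost care.** The contrast with viraemia after lost care therefore largely does not arise there. This stands, but the same restriction is what removes the protection of randomisation.
- **Custody results may not be in the searched systems, and an old result may mislead.** This stands. The documents do not say how often viral load is measured in custody. Because entry needs only a little over three months of ART, a long look-back could return a result from before ART or very early in it and label it as failure in custody.
- **This is one of seven secondary outcomes in a pilot that disclaims effectiveness.** This stands and limits the weight of the point.

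The limitations text in section 5.3.5 mentions disease state as a regression covariate. It does so in a paragraph about a pre/post design and does not name viral load.

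**Conclusion.** The point holds as a missing guarantee. Entry allows viraemia at release, no required form is described as capturing HIV RNA before release, and the planned record search is described for outcomes after release. For all randomised participants the consequence is lost precision and a less interpretable result, not bias. On assumed inputs the precision gain is modest, an interval about 3-13% narrower. The consequence is larger for the Table 3 in-care test, where balance is unprotected and the CAU group might number about 12. The assumed 70-90% baseline suppression and 30-50 point association are illustrative only. The feasibility and acceptability objectives and the self-reported care outcome are unaffected. This is a cheap improvement that is worth making, chiefly because the full trial is intended to use viral load in its primary outcome.

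**What to change.** - In Table 6, mark FV001 X once per participant. Add fields for the most recent pre-release HIV RNA result, its date and the ART start date. If the form already holds these, only the mark and the analysis text need to change.
- Extend the laboratory and tier.net search in section 2.7.3 to the period before release, to fill gaps where custody results are available. Take no new blood sample.
- Count only results taken on ART. Flag those taken soon after ART start, with the cut-off fixed before analysis. Put everyone else in a no-result category.
- Adjust the all-randomised <400 c/mL comparison for pre-release status (<400, ≥400, no result). In the in-care subset, report by pre-release status descriptively, because the CAU numbers may be too small for a three-level adjustment.
- Report loss of suppression among those <400 c/mL before release. Report the proportion with a usable pre-release result as a planning input.

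The cost is a few fields on an existing form, a wider date range on an existing search and some abstraction time. The main downside is an unknown share of participants with no usable result.

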## 5.2 Schedule of case report forms

Table 6: Schedule of data collection within correctional facility

Case Report Form	Form Code	Visits:	Visit 1 Enrolment	Visit 2 Pre-release
		Visit Code:	01.0	02.0
Screening, Eligibility & Enrolment	EL001		X	
Pre-release assessment	RK001		X	
Baseline Demographics	DM001		X	
Visit Contact Documentation	AD001		X	[X]
Pre-release Locator	AD002		X	
Case Note Abstraction Pre-release	FV001		[X]	[X]

X required CRF, [X] may be required if updated or as necessary

Table 7: Scheduled study visit windows for all participants after release from correctional facility

Case Report Form	Form Code	Visits:	Visit 3 Release	Visit 4 Post- release	Visit 5 Post- release	Visit 6 Post- release	Visit 7  Post-release
		Time since release:	0D	30D	900D	182D	90 days from time of entry
		Visit Code:	03.0	04.0	05.0	06.0	07.0
Release verification	AD003		X				
Post-release locator	AD004			[X]	[X]	[X]	
Demographics Follow-Up	DM002			[X]	[X]	[X]	
Health Seeking	SS001			[X]	[X]	[X]	
Clinic Visit	SS002			[X]	[X]	[X]	
HIV/TB Testing	SS003			[X]	[X]	[X]	

No Clinic Visit	SS004			[X]	[X]	[X]	
Post entry into care	SS005						X
Case Note Abstraction Post-release	FV002			[X]	[X]	[X]	[X]
Off Study	AD002			[X]	[X]	[X]	[X]

X required CRF, [X] may be required if updated or as necessary

Visit 7 only occurs if participant had entered into care by Visit 7

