## 2.7.2 Ascertainment of linkage to care

Study staff will contact participants to ascertain care status and update contact information at 30, 90 and 182 days from release. Follow up will primarily be telephonic and will rely on participant self-report. The scheduled visit windows are: Day 30 (from 20-70 days), Day 90 (from 71-150 days), and Day 182 (from 151 – 245). The last contact attempt will be made on Day 246. At the Day 182 visit, participants will be asked for in-person contact that will occur either at research offices or at a site convenient to the participant. This study visit will be used to ascertain visit status, socio-demographic data, and to complete surveys on stigma, social capital, and care satisfaction. In addition, a whole blood sample (8mL) will be obtained for HIV RNA quantification (viral load) if there are no clinic obtained HIV RNA results from within 60 days or 182 days post-release. Refer to schedule of CRFs for data collection tools used at each study visit.

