**Table 2: Feasibility Indicators**

Numerator	Denominator	Measure
-----------	-------------	---------

Number with first TCAC visit	Total in TCAC arm	Proportion
Number in TCAC arm with visit first to a clinic (not TCAC)	Total in TCAC arm	Proportion
Number in TCAC at 6 months (at least 2 visits)	Number with first TCAC visits	Proportion
Number in TCAC at 6 months	Number in TCAC arm	Proportion
Number with no more than two missed visits in 6 months	Number in TCAC arm	Proportion
Proportion of all participants with successful 6month care ascertainment assessed	All study participants	Proportion
Proportion of all participants with 6 m social capital questionnaire and stigma scale	All study participants	Proportion
Proportion among those in care with 6m VL ascertainment	All study participants	Proportion

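### Section 2.7.2 plans stigma and social capital surveys at Day 182, but the form schedule carries none there, and the one listed post-release form that contains them is timed differently by arm

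*Combined protocol and SAP*

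**What the plan says.** Section 2.7.2 describes the Day 182 contact as in person and gives its purpose: "This study visit will be used to ascertain visit status, socio-demographic data, and to complete surveys on stigma, social capital, and care satisfaction". It makes no distinction between arms. It names no form and instead directs staff elsewhere: "Refer to schedule of CRFs for data collection tools used at each study visit".

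The schedule it points to is in section 5.2. Table 7 is headed "Scheduled study visit windows for all participants after release from correctional facility". Table 8 covers the TCAC sessions. Table 5 describes RK002, the post-release assessment, as covering health and ART history, ASSIST, PHQ-9, social capital and stigma, and gives its timing as "CAU - Day 30 visit TCAC- at first session".

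On use of the data, Table 2 includes the indicator "Proportion of all participants with 6 m social capital questionnaire and stigma scale", with all study participants as the denominator. Section 2.9.2 lists change in social capital score and change in stigma index score as secondary outcomes. Table 3 tests the score, not the change, by arm with a Wilcoxon rank sum test. Neither place gives a time point.

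**The concern.** Field staff work from the form schedule, and section 5.3.1 builds one REDCap form per paper CRF. If the schedule omits a survey that the text plans, the survey may not be done, or may be done in one arm or at one site only.

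The analyst then faces a second problem. With no time point fixed for the score outcomes, the post-release scores most readily at hand would be those from RK002 as Table 5 schedules it. Comparing arms on those data would set CAU at about Day 30 against TCAC at whatever date a participant first attended, and only among those who attended. Attendance follows randomisation and is part of what the intervention is meant to change, so this would no longer be a comparison of the randomised groups.

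**Working it through.** **Step 1. Is there a scheduled form for the 6-month scores?**

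- Section 2.7.2: surveys at Day 182 (window 151–245 days).
- Table 7: release verification, post-release locator, demographics follow-up, health seeking, clinic visit, HIV/TB testing, no clinic visit, post entry into care, case note abstraction and off study. RK002 and the laboratory form LT001 appear in no column.
- Table 8: only routine health screening (RK003) and TCAC transition (TR001), months 1 to 6.
- Table 5: RK002 is the only post-release form described as containing social capital and stigma. It has one time per arm, and neither is 6 months.
- Table 6: the baseline counterpart, RK001, is required at enrolment in both arms, so a baseline for a change score exists.

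The text plans a Day 182 survey, and the schedule it defers to provides no form for it.

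**Step 2. How different is the timing if RK002 is used?**

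The Day 30 window is 20–70 days. The Day 182 window opens at day 151. A CAU score from the Day 30 visit is therefore at least 151 − 70 = 81 days earlier than any score in the Day 182 window. The first TCAC session has no fixed day, and participants who never attend never reach it.

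**Step 3. How many TCAC participants could be left out?**

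The documents give no first-session attendance rate. The nearest figure is the 40–66% transition in section 4.1, which the plan uses to size four clubs of 12–20. It reproduces: 120 × 0.40 / 4 = 12, and 120 × 0.66 / 4 = 19.8, about 20. It is therefore a club-size assumption. Taking it, as my assumption, to approximate first-session attendance:

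- With an RK002: 120 × 0.40 = 48 to 120 × 0.66 = 79.
- Without one: 120 × (1 − 0.66) = 41 to 120 × (1 − 0.40) = 72.

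**Step 4. What would a common Day 182 survey give?**

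Applying the plan's 75% follow-up target (section 4.2.1) or 78% ascertainment (section 4.1) to survey completion in both arms, again as an assumption:

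- TCAC: 120 × 0.75 = 90 to 120 × 0.78 = 94.
- CAU: 60 × 0.75 = 45 to 60 × 0.78 = 47.

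Both arms would then be measured in the same window, with no condition on club attendance. The power statement in section 4.1 concerns a binary outcome and is not affected.

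**The case against.** The strongest reply is that the measurement is planned. Section 2.7.2 states it without restriction by arm, section 2.9.1 lists use of these tools among its feasibility considerations, and Table 2 specifies 6 months with all participants as the denominator. Section 2.8.9 adds that the first-session screens in TCAC guide referrals and services. A reader might infer from the tables that the Day 30 or first-session survey is the only one after release, or that the 6-month scores cannot be measured. The documents do not support either reading. What is missing is the link from that intention to a form, a visit column and an analysis time point.

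Three further replies have force.

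- **Viral load.** A reader might extend the point to HIV RNA because LT001 is absent from Table 7. That goes too far. Sections 2.7.2, 2.7.4 and 2.8.9 plan 6-month viral loads, section 2.9.2 draws first on clinic and laboratory records, and Table 5 lists LT001 after release for both arms. Only a schedule row is missing.
- **Primary outcome forms.** SS001 and SS002 carry only a conditional mark at Day 182. For SS002 this is sensible, because it records details of clinic visits that a participant reports. SS001 asks about health seeking in general and has less reason to be conditional.
- **Size.** The 41–72 range describes an analysis that the plan does not state, and it rests on a club-size figure. CAU would not be complete at Day 30 either, since that contact can fail too. The difference is that the TCAC losses would depend on attending the intervention.

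The practical stakes are also limited. The survey-completion indicator has no a priori target, and section 4.1 says that this is not an effectiveness study.

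**Conclusion.** The point holds as a contradiction between section 2.7.2 and the form tables, made worse by the missing time point in section 2.9.2 and Table 3. It touches two of seven secondary outcomes and one Table 2 indicator under the first primary objective.

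There are two consequences, depending on what is done. If the schedule is followed literally, no 6-month social capital or stigma score is collected in either arm. If RK002 is used as Table 5 times it, the arms differ in timing and in selection. The TCAC loss would be about 41 to 72 of 120, but only if 40–66% approximates first-session attendance. The contradiction itself does not depend on that assumption.

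It should be corrected because the risk is avoidable at almost no cost. It does not threaten the primary outcome or the sample size.

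**What to change.** - **Table 7, Visit 6 (Day 182):** add the social capital and stigma sections of RK002 as required for both arms, and amend the RK002 row of Table 5 to match. Adding the whole of RK002 would bring in ASSIST, PHQ-9 and health history, which section 2.7.2 does not list for that visit. The care satisfaction survey in section 2.7.2 is not described under any form in Table 5, so name its form at the same time.
- **Section 2.9.2 and Table 3:** define both score outcomes as Day 182 minus baseline RK001 in both arms, and use the same term, score change, in both places. State that the Day 30 or first-session RK002 is not used for the between-arm comparison.
- **Secondary tidying in Table 7 at Day 182:** add LT001 with the conditional mark, consistent with the conditional draw in section 2.7.2. Mark SS001 as required. Leave SS002 conditional on a reported clinic visit.

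The cost is edits to Tables 3, 5 and 7 and a sentence or two in section 2.9.2. No extra visit is needed, because the in-person Day 182 contact is already planned, and the social capital and stigma instruments are already in use at baseline.
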